9.4 STATISTICAL ANALYSES

9.4.1 GENERAL APPROACH

All primary analyses will be performed as intent-to-treat analyses with a type I error rate of 10% (two-sided). Parametric distributional assumptions will be checked. If assumptions fail, other distributions will be considered prior to transformations and non-parametric methods. SAS (version 9.4) or the latest version of R (currently 3.6.3) will be used to analyze the data.

9.4.2 ANALYSIS OF THE PRIMARY EFFICACY ENDPOINT(S)

The primary analysis will be according to intent-to-treat and conducted using ANCOVA, adjusting for baseline \log_{10} viral load (or conversion from Ct value assuming $1 \log_{10} = 3.3$ Ct units). We will use the t-statistic for the treatment effect to determine whether the treatment is statistically different from the placebo at the overall 10% level of significance, controlling for baseline \log_{10} viral load. Because of the interim analysis (see below), a p-value of 0.06 (2-sided), corresponding to an efficacy boundary value of 1.875 at the last look, will be used for the level of significance for the primary outcome at the final analysis. In sensitivity analyses, we will also adjust for age and time since onset of symptoms. We will also conduct a per-protocol analysis as a secondary analysis. We will assess the missing mechanism and the impact of missing data. Sensitivity analyses under either missing at random or missing not at random will be considered, as appropriate.

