9 STATISTICAL CONSIDERATIONS

9.1 STATISTICAL HYPOTHESES

All tests performed will be tests of superiority.

For the primary endpoint, we will test the hypothesis that camostat mesylate results in a significantly greater change from baseline to day 4 in respiratory (Nasopharyngeal swab, saliva RT-PCR) \log_{10} viral load compared to placebo.

Similarly, for secondary endpoints we will test the hypothesis that camostat mesylate will result in a significantly greater change from baseline to days 2 and 6 in respiratory (nasopharyngeal swab, saliva RT-PCR) \log_{10} viral load compared to placebo; that camostat mesylate will reduce \log_{10} of a positive COVID19 test at days 2 and 6 (optional swabs), rate of positive tests at days 6, 14 (required), and 28 (required); and that camostat mesylate will result in lower symptom burden at days 6 and 14.

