9.4.6 PLANNED INTERIM ANALYSES

Interim monitoring for safety, efficacy and futility will be conducted. When 50% of the participants have accumulated the primary endpoint, we will conduct an interim analysis to assess for efficacy and futility using the group sequential method with asymmetric boundaries. We will use a Pocock boundary for efficacy and will consider stopping early for efficacy if the t-statistic for the treatment effect is greater than the critical value of 1.875; we propose stopping for futility if the drug is trending in the wrong direction, and have set a futility boundary value of -1. Safety will be assessed by comparing the rate of adverse events in the treatment group using Type I error of 5% (2-sided); no control for multiplicity will be done for safety outcomes.

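### The stated overall two-sided 10% type I error does not match the asymmetric bounds, which give 5.6% or 8.0% (5.0% on the efficacy side); the design is better described as one-sided 5% superiority

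*Combined protocol and SAP*

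**What the plan says.** Two descriptions of the primary test stand side by side.

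- **Two-sided.** Section 9.4.1: "All primary analyses will be performed as intent-to-treat analyses with a type I error rate of 10% (two-sided". Section 9.2 sizes the trial on the same two-sided 10% error. Section 9.4.2 has the t-statistic determine "whether the treatment is statistically different from the placebo at the overall 10% level of significance", and sets the final criterion as "a p-value of 0.06 (2-sided), corresponding to an efficacy boundary value of 1.875 at the last look".
- **One direction.** Section 9.1: "All tests performed will be tests of superiority", with the primary hypothesis worded as a greater change on camostat. Section 9.4.6 describes asymmetric group sequential boundaries at 50% information: the team "will consider stopping early for efficacy if the t-statistic for the treatment effect is greater than the critical value of 1.875". On the other side, "we propose stopping for futility if the drug is trending in the wrong direction, and have set a futility boundary value of -1".

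Section 9.4.6 gives no lower rejection bound at the interim. The plan does not say whether the futility bound is binding, and it states no one-sided alpha.

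**The concern.** The value 1.875 is the Pocock constant for an overall two-sided 10% level only when both looks can reject in both directions. Section 9.4.6 removes the lower rejection region at the interim and also ends trials that fall below -1, most of which would have supplied the lower-tail rejections at the end. The level quoted in 9.2, 9.4.1 and 9.4.2 is therefore not a property of the design in 9.4.6.

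Two things are at stake. Type I error is a headline figure that will be copied into the trial report. And a test described as one of difference suggests that the trial could conclude camostat worsens viral load, when that ability depends almost entirely on whether the -1 bound is obeyed.

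**Working it through.** **Inputs.** One interim at 50% information, upper bound 1.875, futility bound -1 (9.4.6). Final bound 1.875, two-sided (9.4.2). A positive statistic favours camostat. (Z1, Z2) is taken as bivariate normal with correlation √0.5 = 0.707.

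**1. Reproduce the plan's constant.** Solving P(|Z1| > c or |Z2| > c) = 0.10 gives c = 1.8754; at 1.875 the probability is 0.1001. The nominal level is 2 × (1 − Φ(1.875)) = 0.061, quoted as 0.06. The same constant, 1.8754, solves the one-sided 5% problem P(Z1 > c or Z2 > c) = 0.05.

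**2. Upper tail under the null, plan's rules.** P(Z1 > 1.875) + P(−1 ≤ Z1 ≤ 1.875, Z2 > 1.875) = 0.0304 + 0.0196 = 0.0500. Ignoring the futility bound changes this only in the fifth decimal place.

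**3. Lower tail under the null.**
- Futility obeyed: P(−1 ≤ Z1 ≤ 1.875, Z2 < −1.875) = 0.0064.
- Futility overridden: P(Z1 ≤ 1.875, Z2 < −1.875) = 0.0304.

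**4. Totals against the stated 10%.**

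| Rule | Upper | Lower | Total |
|---|---|---|---|
| ±1.875 at both looks | 5.0% | 5.0% | 10.0% |
| Plan, futility obeyed | 5.00% | 0.64% | 5.6% |
| Plan, futility overridden | 5.00% | 3.04% | 8.0% |

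Eight million simulated trials gave 5.65% and 8.05% for the last two rows. Using p < 0.06 exactly (1.881) at the final look gives 5.60% and 7.97%.

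**5. Sensitivity to timing.** With the interim at 40% or 60% information, the totals are 6.1% or 5.2% (obeyed) and 8.2% or 7.8% (overridden).

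**6. Ability to declare camostat worse.** Assume a true effect of d = 0.6 in the wrong direction. This is the size of the example in 9.2, (4 − 1)/5.0 = 0.6, with its sign reversed. Assume 103 evaluable, from 114 × 0.9 = 102.6. The mean of Z2 is −0.6 × √(103/4) = −3.04, and the mean of Z1 is −3.04 × 0.707 = −2.15.
- Stopped at −1: Φ(−1 + 2.15) = 88%.
- Declared different, futility obeyed: 6.3%.
- Declared different, futility overridden: 88%.
- Symmetric Pocock ±1.875 at both looks: 89%.

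**7. Sample size.** One-sided 5% and two-sided 10% share the critical value 1.645, and both give 48 per arm by the normal approximation. The plan's 98 in total gives 90.4% power by the noncentral F calculation, so it stands under either label.

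**8. Interval.** An ordinary 90% interval uses 1.645. Under the null, the probability of reaching the final look with Z2 between 1.645 and 1.875 is 1.6%. Those trials would show an interval excluding zero beside a failed test. The coverage matching 1.875 is 2Φ(1.875) − 1 = 93.9%.

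**The case against.** The best defence is that two-sided 10% is ordinary shorthand for 5% in each direction. A reader who sees it expects a 5% risk of a false efficacy claim, and the design delivers 5.0%. The realised error is below the stated level, leaving futility stopping out when setting the efficacy bound is normal conservative practice, and 9.4.6 openly calls the boundaries asymmetric. All of this stands.

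A reader might infer that the efficacy false-positive rate is misreported, that alpha is inflated, or that the bounds or sample size must change. The documents support none of these: steps 2 and 7 show that the efficacy error and the sample size are as intended.

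A reader might also infer that the trial cannot detect harm. That goes too far. The 6% figure assumes the -1 bound is always obeyed; if it is overridden the figure is 88%, almost that of a symmetric design. The plan never sets out to establish harm on viral load: section 2.1 says only that the drug would not be pursued if viral load is not reduced. Adverse events are compared separately at two-sided 5%, including at the interim.

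What the defence does not answer is that 9.4.2 goes beyond shorthand. It names an overall level and a test of difference, and the rules in 9.4.6 supply neither in full. The adverse-event comparison does not address worsening of viral load.

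**Conclusion.** The stated overall two-sided 10% level is not a property of the specified design. The total is 5.6% with futility obeyed and 8.0% with it overridden, and the efficacy side is 5.0% in both cases. The plan is a hybrid: one-sided at the interim, two-sided at the final look. The error is one of labelling and is conservative. Its practical consequence is confined to the reported level and to what can be concluded when results run against camostat, which the plan leaves open by not saying whether -1 is binding.

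The figures assume normal statistics and an interim at exactly 50% information. With a t reference, 1.875 corresponds to a two-sided p of about 0.066 at 54 degrees of freedom and 0.063 at 111, a small shift that leaves the finding unchanged. The harm figures rest on the assumed d = 0.6 and 103 evaluable participants.

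**What to change.** - In 9.2, 9.4.1 and 9.4.2, state the primary test as one-sided 5% superiority, with upper bound 1.875 at both looks and a non-binding futility bound of -1. Calling it non-binding costs no efficacy alpha, since the upper tail is 5.0% either way.
- In 9.4.2, replace the two-sided p-value of 0.06 with the matching one-sided nominal level of about 0.03 (1 − Φ(1.875) = 0.030), and remove the phrases describing an overall 10% level and a test of difference.
- In 9.4.6, say that crossing -1 is a futility stop and not a conclusion of harm.
- For the primary endpoint, report an interval consistent with the bound: about 94%, or a group-sequential-adjusted 90% interval. Do not carry over the ordinary 90% interval used for symptom scores in 9.4.3.
- Section 9.4.3 tests secondary endpoints at two-sided 10% using the same ANCOVA for viral load. Add a sentence saying that this differs from the primary test.

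The cost is wording only: bounds, sample size and schedule are unchanged. The trial gives up a nominal final-look claim in the harm direction. If the sponsor does want a true two-sided 10% test, the alternative is to add a rejection bound of -1.875 at the interim and to continue past -1 unless it is crossed.

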4.2 SCIENTIFIC RATIONALE FOR STUDY DESIGN

The rationale for placebo is that there is no known effective treatment for COVID-19 disease. The natural history of viral shedding in infected patients varies substantially among patients. Generally viral replication appears within about 5 days after exposure, and an asymptomatic phase may or may not be present for days prior to the onset of symptoms, most often described as progressive symptoms of fever, cough, malaise and shortness of breath. Because there is no available animal model in which to study the anti-SARS-CoV-2 viral effect of camostat mesylate, infected humans must be studied. Because respiratory viral burden varies substantially (orders of magnitude ranging from 10^2 - 10^9 /swab) among COVID-19-affected individuals, in order to demonstrate an antiviral effect of any drug on SARS-CoV-2, serial samples and measurement of viral load on respiratory samples must be compared between placebo and experimental groups. We will also perform viral load testing on saliva because recent studies have suggested that saliva may be more reliable; however the nasopharyngeal swab remains the gold standard. Because enrollment will be based on an initial positive COVID-19 test on a nasopharyngeal swab and participants randomized in a double-blinded way, experimental and placebo groups are expected to be comparable without bias.

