5 STUDY POPULATION

5.1 INCLUSION CRITERIA

Consecutive participants testing positive for COVID-19 at the Sargent Drive testing center, any other YNHHS site, or external COVID-19 testing facility will be eligible for enrollment.

In order to be eligible to participate in this study, an individual must meet all of the following criteria:

1. Be enrolled within 3 days of being notified of their first positive COVID-19 test result.
2. Evidence of a recent active COVID-19 infection, as evidenced by the positive test results being associated with at least one COVID-19-compatible symptom such as fever, upper respiratory symptoms, cough, chills, loss of taste/smell, etc.(see COVID-19-PRO symptom score sheet), or a recent high-risk exposure to COVID-19
3. Provision of informed consent
4. Stated willingness to comply with all study procedures and availability for the duration of the study
5. Male or female, aged 18 and older
6. Diagnosed with COVID-19 within past 3 days and not exhibiting manifestations requiring hospitalization such as extreme shortness of breath or severe prostration. Nurses at the study site will assess such severe conditions requiring hospitalization, which would preclude enrollment.
7. Ability to take oral medication and be willing to adhere to the camostat mesylate regimen.
8. For men and women of reproductive potential: use of condoms or other methods to ensure effective contraception with partner during study drug administration.
9. Agreement to adhere to Lifestyle Considerations (birth control measures) throughout the 7-day duration of study drug administration.
10. English and Spanish speaking subjects as well as patients speaking any language for which we can find appropriate translators will be enrolled. A short form with interpretation will be used for anyone speaking a language for which a translated informed consent form is not currently available in accordance with local site IRB policies, including developing certified translations as necessary.

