9.2 SAMPLE SIZE DETERMINATION

The sample size calculation is based on the primary outcome of interest: change in \log_{10} respiratory (nasopharyngeal swab, saliva swab RT-PCR) viral load from baseline to day 4 post-randomization. Given the limited data on the variability of the change in \log_{10} viral load, we have powered the study based on detecting a moderate standardized effect size of 0.3 using an analysis of covariance (ANCOVA), adjusting for baseline \log_{10} viral load. To put into context, one scenario that would produce a 0.3 standardized effect size would be a change of 4 in \log_{10} viral load in the camostat mesylate group compared to a change of 1 in \log_{10} viral load in the placebo group assuming a standard deviation of 5.0. (NOTE: For ANCOVA, the effect size is the standard deviation of the treatment means divided by the pooled standard deviations of the observations.) To be conservative we assume a R-squared of 0 between the \log_{10} viral RNA at 4-days and baseline \log_{10} viral RNA. With a power of 90%, and a type I error rate of 10% (2-sided), we would be able to detect the hypothesized 0.3 standardized effect size with 98 total patients - 49 patients per group with a 1:1 randomization. Increasing this sample size by 15%, 5% for an efficacy and futility look at 50% information (i.e. when half of the patients have been enrolled) and 10% to account for loss to follow up, gives a total of 114 participants (57 per treatment arm).

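### Age and time since symptom onset are left to a sensitivity analysis, and onset time has no definition for asymptomatic participants: a cheap, minor improvement to the primary ANCOVA

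*Combined protocol and SAP*

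**What the plan says.** Section 9.4.2 specifies an intention-to-treat ANCOVA of the day-4 change with baseline log10 viral load as the only covariate. The wider model appears only as a sensitivity analysis: "we will also adjust for age and time since onset of symptoms". The same section promises to assess the missing-data mechanism, with sensitivity analyses under missing at random or missing not at random as appropriate. It names no covariate and no method.

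Inclusion criterion 2 (Section 5.1) requires a positive test together with at least one compatible symptom, "or a recent high-risk exposure to COVID-19". Exclusion criterion 3 (Section 5.2) removes positives without a known recent exposure. An exposed person without symptoms is therefore eligible.

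Section 4.2 says: "The natural history of viral shedding in infected patients varies substantially among patients". It adds that load per swab spans several orders of magnitude and that an asymptomatic phase may precede symptoms. Section 4.1 states that there is no stratification.

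Section 9.2 sizes the trial with no credit for covariates: "To be conservative we assume a R-squared of 0".

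No section states that an onset date is recorded. The Schedule of Activities (Section 1.3) lists demographics and medical history, and the symptom tool described in Section 9.4.3 covers severity, frequency and highest temperature.

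**The concern.** There are two linked issues.

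**Unused information.** Two participants with the same baseline load may be on the rising or the falling part of the viral course. Time since onset can help to tell them apart; a single baseline load cannot. Entry is limited by time from notification or diagnosis, not by time from onset, so onset time may vary widely between participants. With unstratified randomisation, nothing but chance balances it between arms. The sponsor already regards age and onset time as relevant enough to prespecify. At stake is some precision and some protection against chance imbalance.

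**An undefined covariate.** An asymptomatic participant has no onset date at day 0. Standard ANCOVA software omits any row with a missing covariate. If the sensitivity model were fitted that way, it would differ from the primary in both covariates and population, and a difference between the two results could come from either.

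**Working it through.** **1. Reproduce the planned sample size.** Inputs from Section 9.2: power 90%, two-sided type I error 10%, effect size f = 0.3, R-squared 0. The effect size is defined there as "the effect size is the standard deviation of the treatment means divided by the pooled standard deviations of the observations". With two equal arms f = d/2, so d = 0.6. The worked scenario agrees: changes of 4 and 1, "assuming a standard deviation of 5.0", give (4 - 1)/5 = 0.6.

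Power of the ANCOVA F test with one covariate: 1 numerator and N - 3 error degrees of freedom, noncentrality N × 0.3².

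- N = 96: 0.8985
- N = 98: 0.9038

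So 98 is the smallest even N that reaches 90%, as stated. The plan inflates this to 114.

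**2. Unadjusted power with the interim look.** Evaluable N = 114 × 0.90 = 102.6, taken as 102. There are two looks, at half and full information, with efficacy boundary 1.875 and futility boundary -1 (Sections 9.4.2 and 9.4.6). The efficacy boundary was converted to its two-sided p-value (0.061) and applied on the t scale. Simulated power is about 0.885. Applying 1.875 directly to the t-statistic gives about 0.89.

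**3. Power with the covariates added.** If they explain a share R² of the residual variance, the standardised effect becomes 0.6/√(1 - R²). Three extra degrees of freedom are charged: age, time since onset and a symptom indicator. The documents give no R², so the range is an assumption.

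| Assumed R² | Two-look power, N = 102 | Equivalent gain in N, 1/(1 - R²) - 1 |
|---|---|---|
| 0 | 0.885 | 0% |
| 0.05 | 0.899 | 5% |
| 0.10 | 0.913 | 11% |
| 0.15 | 0.926 | 18% |

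At R² = 0 the three degrees of freedom cost almost nothing: power stays at 0.885 to three decimals.

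**4. What a complete-case fit would do to the sensitivity model.** The asymptomatic share is not given, so this too is an assumed range. Start from 98 evaluable, three covariates, d = 0.6, no precision gain credited, single-look F test.

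| Assumed asymptomatic share | Participants left | Power, alpha 0.10 | Power, alpha 0.06 |
|---|---|---|---|
| 0% | 98 | 0.90 | 0.86 |
| 5% | 93 | 0.89 | 0.84 |
| 10% | 88 | 0.87 | 0.82 |
| 20% | 78 | 0.84 | 0.77 |
| 30% | 69 | 0.79 | 0.72 |

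These losses fall on the sensitivity model only. The primary model's N and power do not change.

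**The case against.** The strongest reply is that a parsimonious primary model with wider adjustment in sensitivity is legitimate. That stands. A reader might infer that omitting onset time biases the primary result; randomisation rules out systematic bias, no stratification factor is left out, and baseline load is already in the model.

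A reader might also infer that the trial is underpowered without these covariates. The documents do not support that. The figure of 0.885 arises only under the deliberately conservative R-squared of 0. If baseline load alone explained about 4-5% of the variance, two-look power would already be about 0.90. The 0-15% range has no source in the documents.

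Two further inferences go too far. Onset date cannot be called already collected: the planned analysis implies it, but nothing states it. Nor does the plan say that asymptomatic participants will be dropped; that is default software behaviour, and Section 9.4.2 makes a general commitment on missing data. That commitment does not settle the matter, however, because missing-data methods address values that exist but were not observed. Even if participants were dropped, comparison would not be lost: refitting the baseline-only model on the same subset separates the two effects.

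Finally, promoting an undefined and possibly unrecorded variable could put the primary analysis at risk, and substituting days since first positive test would place two clocks under one slope. Section 5.1 limits enrolment to 3 days from notification or diagnosis, so that second clock has little range. These are fair conditions on the remedy, and the fix below meets them.

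**Conclusion.** The point holds as a cheap, minor improvement. It is not an error in the primary analysis.

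The documents establish that age and time since onset are named but kept out of the primary model, and that onset time has no definition for a group that the inclusion criteria admit. That the sensitivity model would exclude this group is conditional on a complete-case fit.

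The gain is conditional on the assumed R²: from nothing at 0 to about 4 percentage points of power at 0.15 (0.885 to 0.926, for d = 0.6 and 102 evaluable participants). The number affected by the missing definition cannot be computed, because the asymptomatic share is not given.

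**What to change.** Finalise the wording before the interim look, not merely before final unblinding, because the interim boundary in Section 9.4.6 is applied to the same treatment t-statistic.

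- **(a) Record.** Confirm that symptom status and onset date are recorded at day 0; add a case report form item if they are not.
- **(b) Define.** Give every participant a symptomatic/asymptomatic indicator as of day 0, plus days since onset, set to a constant when asymptomatic. The indicator absorbs the choice of constant, and two clocks do not share one slope. State a simple rule for a symptomatic participant with no usable onset date, applied without reference to treatment arm, so that nobody leaves the intention-to-treat set for lack of a covariate.
- **(c) Model.** Include age and this covariate in the primary ANCOVA, keep the baseline-only model as the sensitivity analysis, fit both to the same participants, and report the number in each.

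The cost is SAP wording, up to three degrees of freedom and possibly one case report form item. If the sponsor prefers to keep the baseline-only primary model, (a), (b) and the same-participants rule are still needed to make the sensitivity analysis interpretable.
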